C) This would be a randomized, double-blind, placebo controlled trial. 1/2 of the patients would receive intra-operative secretin, the other half would receive saline placebo. Both the surgeon and patient would be blinded to the randomization assignment. The advantage of giving secretin would be that it may allow for the identification of a leak intra-operatively and subsequently allow for repair if the leak was identified prior to abdominal wall closure. While the safety profile of the drug is excellent, receiving the medication could theoretically cause an increased intraductal pressure which may cause a leak when one was not already present.

D) Human subjects are needed to evaluate intra-operative, intravenous secretin in patients undergoing pancreatic duct resection.

4. Design, procedures, materials and methods:

Use a level of detail similar to what would be used when submitting an article for publication in a peer reviewed journal. Explain the study procedures, data collection, and analysis process. Please define terms and explain concepts which might be confusing to reviewers who are not expert in the area of the study. If a formal protocol for the study exists, page references to the protocol are acceptable.

This study design is a prospective, double-blind, randomized-controlled trial. We will enroll patients in our institution undergoing pancreatic resection to receive either 1) one dose weight-based Secretin to be given once the closure of the pancreatic resection margin is complete 2) saline placebo.

Consent and basic demographics will be garnered by the physician in an office visit once the surgery has been scheduled and consent for the surgery is being obtained. The consent will be validated by the treating surgeon in the pre-procedure area on the day of the surgery.

The patient will undergo the scheduled surgery. Once the pancreatic anastomosis has been deemed acceptable by the attending physician, but prior to abdominal closure, the patient will be randomized to receive either Secretin (0.2 mcg/kg) or saline placebo. The attending surgeon will be blinded to this assignment.

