10 minutes after receiving the Secretin or placebo, the attending surgeon will examine the anastomosis or repaired cut edge of the pancreas to determine if leakage of pancreatic fluid is noted, leak location(s), type (side branch/main duct), color of the fluid and whether any further intervention was performed in an effort to close the leak. Specifics of operative intervention will be documented. The patient will then undergo standard surgical closure of the abdomen.

As is standard of care at DHMC, surgical drains will be placed adjacent to the anastomosis and drain amylase output will be checked on POD #1 through POD#5. Pancreatic leak is defined according to the International Study Group of Pancreatic Fistula (ISGPF) definition as a clinically relevant postoperative pancreatic fistula is now redefined as a drain output of any measurable volume of fluid with an amylase level >3 times the upper limit of institutional normal serum amylase activity, associated with a clinically relevant development/condition related directly to the postoperative pancreatic fistula. Randomization assignments will be revealed once the patient has been discharged from the hospital following their initial surgical intervention. A follow-up visit with the patient two weeks following discharge, will evaluate for any evidence of ongoing pancreatic duct leak.

The patient will also be followed for thirty (30) days after secretin/placebo administration by the research team to assess for a pancreatic leak and sequelae of a leak, - intra abdominal deep soft tissue infection, surgical site infection, hemorrhage, IR (interventional radiology) drain placement, or reoperation. This will be accomplished by telephone and/or by chart review Patients discharge date will be followed for the study. If no secretin/placebo is administered, the patient will not be followed on the study.

If any of the above are noted during the 30 days following secretin/placebo administration the following will be used to assess causality:

Causality

The following 4-point scale will be used for rating the causal relationship of the AE to the investigational product:

Unrelated: Clearly and incontrovertibly due to extraneous causes, and does not meet criteria listed under unlikely, possible, or probable.

- Unlikely:** Does not follow a reasonable temporal sequence from administration. May have been produced by the patient's clinical state or by environmental factors or other therapies administered.

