- Possible:** Follows as reasonable temporal sequence from administration. May have been produced by the patient's clinical state or by environmental factors or other therapies administered.
- Probable:** Clear-cut temporal association with improvement or cessation of test drug or reduction in dose. Reappears upon re-challenge. Follows a known pattern or response to test drug.

The primary outcome of interest will be the presence of pancreatic leaks based on the amount of drain amylase on or after POD#3. Secondary outcomes will include: 1) technical interventions intraoperatively directed to leak closure or manipulation of the anastomosis following Secretin or placebo stimulation 2) length of stay as a surrogate to complication severity after pancreatic surgery.

Patient demographics, risk factors, operative technique, randomization assignment and outcome data will be recorded on standard case report forms – **See Case Report Forms in Appendix**. Data will be stored in an encrypted hard-drive by a single agent ([name]) who is the only researcher who has access to the randomization data.

5. Inclusion/Exclusion Criteria:

Please provide detailed description of inclusion and exclusion criteria. If a formal protocol for the study exists, page references to the protocol are acceptable.

Inclusion criteria:

1. Scheduled for pancreatic surgery requiring pancreatic resection at DHMC
2. Age greater than 18 years old
3. Ability to provide written informed consent

Exclusion criteria:

1. Inability to provide written informed consent
2. Current ongoing acute pancreatitis
3. Pregnant or nursing mothers
4. Any medical condition which in the judgment of the Investigator renders participation in this study medically inadvisable.
5. Participation in an investigational clinical study for a drug or medical device within 30 days prior to Visit 1.
6. [Any known allergy to methylene blue.](#)

6. Financial Considerations:

Disclosure of financial impact on the participant is critical to informed consent. Insurance cannot be billed for research-related services outside the standard of care or paid for by the funding agency for

the study. The department, the study or the participant may be responsible for payment for research-related services. Participants should know which tests, visits, or procedures will be billed to them or their insurance and which ones will be paid by the funding agency for the study or the department.

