c) *Describe reasons for requesting that DHMC or Dartmouth College provide coverage for research-related injury or illness, which is not standard policy.*

NA

29. Participant Remuneration:

Will participants be paid for their time, reimbursed for travel or meal expenses, or receive any sort of "gift" for participating in this study?

Yes No

If yes, please describe in detail:

Note: Participant remuneration is not considered a benefit of being in a research study. CPHS will consider the amount of payment in relation to the time needed and any inconvenience to participants. Payment, reimbursement, or gifts should not be in an amount that would be coercive to the participant population.

If study is to be done at the VA, specific questions need to be answered if a participant is being paid "in excess of reimbursement for travel." Please contact the CPHS office if you need more information.

30. Use of Drug or Biological Agent:

Respond to items below or check x No drug or biological agent involved.

List the drugs and biologic agents to be used in this study: Secretin (0.2 mcg/kg) in a single dose

Is each drug or biological agent approved by the FDA for the specific indication for which it is used in this study?

Drug or Biologic Agent: Secretin Yes **This drug is an FDA designated orphan drug "for use in conjunction with diagnostic procedures (excluding ERCP) for pancreatic disorders to increase pancreatic fluid secretions." In this study, secretin is being used under an IND granted to ChiRhoClin.**

Drug or Biologic Agent: _____ Yes No

If no, respond to a and b for each drug or biologic agent used for an unapproved indication:

a) *Briefly discuss the plan for the storage, dispensing, handling, and disposal of investigational and FDA-approved drugs, devices, and biologics. When these activities are being done by the investigator, include a description of the procedures for inventory control and documentation.*

DHMC Investigational Pharmacy is managing all study drugs.

Yes No

If No please describe management plan below.

b) Check and respond to one of the following statements for each drug or biologic agent:

If this study is being done under an Investigational New Drug (IND) application to the FDA please provide: IND # (Investigational New Drug): # 56821 and specify who holds the IND#: ChiRhoClin, Inc.

OR

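### Two of the three elements that define a 'Probable' causality grade cannot be observed after a single intra-operative dose, and the protocol does not say how the elements combine

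*Combined protocol and SAP*

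**What the plan says.** Section 4 gives each patient in the active arm "one dose weight-based Secretin to be given once the closure of the pancreatic resection margin is complete", and section 30 confirms "Secretin (0.2 mcg/kg) in a single dose". The research team then follows patients for 30 days for a leak and its sequelae: deep or surgical-site infection, hemorrhage, radiological drain placement and reoperation.

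The causality instruction reads "If any of the above are noted during the 30 days following secretin/placebo administration the following will be used to assess causality", and the scale is introduced by "The following 4-point scale will be used for rating the causal relationship of the AE to the investigational product". The grades are Unrelated, Unlikely, Possible and Probable. Probable is defined by three statements set one after another: the first two are "Clear-cut temporal association with improvement or cessation of test drug or reduction in dose. Reappears upon re-challenge" and the third is "Follows a known pattern or response to test drug". No conjunction joins them, and nothing says whether all or any must be met.

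Section 4 also says that the assignment is revealed once the patient leaves hospital after the initial operation.

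**The concern.** Stopping, dose reduction and re-challenge are criteria for a drug given repeatedly. Here the drug is given once, and exposure is over before any graded event is known. A top grade that depends on those criteria may be out of reach, and the scale would then lose its ability to mark an event as more than possibly related.

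This matters because section 3(C) names a way in which the drug could do harm: "receiving the medication could theoretically cause an increased intraductal pressure which may cause a leak when one was not already present". A leak is among the events to be graded. Almost every post-operative leak follows the infusion in time and could also be explained by the operation, so grades will tend to collect at Possible. The safety record would then hardly separate a strongly suspected drug effect from an ordinary surgical complication.

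**Working it through.** There is no figure to reproduce, so the check sets the definitions against the dosing schedule.

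**Step 1: which elements of Probable can be observed after one dose?**

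| Element | Needs | Observable here? |
|---|---|---|
| Timing tied to improvement, stopping or dose reduction | Ongoing dosing that can be stopped or lowered | No: dosing is complete after one administration |
| Return on re-challenge | A second exposure | No: none is planned |
| Known pattern or response | Knowledge of the drug's effects | Yes |

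Section 14 mentions a small test dose when discussing allergic risk. It does not supply a re-challenge: it is not among the section 4 procedures, and it could not test whether a leak, infection or reoperation recurs.

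**Step 2: what follows if all elements are required?** Re-challenge alone closes the grade. The usable scale shrinks from four grades to three, with Possible as the ceiling.

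The neighbouring grades support this cumulative reading. Unlikely and Possible carry the same second sentence, on the patient's clinical state, environment and other therapies. They differ only in the first, which for Possible is "Follows as reasonable temporal sequence from administration" and for Unlikely is its negation. If any one sentence were enough, the shared sentence would put an event in both grades at once. Those two grades work only when their sentences are read together, and it is natural to read Probable the same way.

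**Step 3: what follows if any one element is enough?** Probable stays reachable through the third element, but the route is narrow and uncertain for the events being graded. Section 14 reports no adverse drug reaction beyond rare transient flushing, and section 3(C) calls a secretin-induced leak theoretical. One rater could say that no known pattern exists and stop at Possible. Another could say that increased pancreatic secretion is a known response and grade the same leak Probable. The text settles neither the combination rule nor this question.

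**Step 4: when is the grade given?** Graded events run to 30 days after administration, but the assignment is revealed at discharge. Section 4 does not say who grades or when. An event that arises after discharge may therefore be graded with the arm known.

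**Step 5: what uses the grade?** Nothing in section 7 does: the primary comparison is a two-tailed Fisher's exact test on leak, and the 88 per arm is based on leak rates of 20% and 5%. Section 8 does not either: the interim look at 88 patients goes to a formal comparison if more than 66% of leaks fall in one group.

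**The case against.** The strongest reply is that Probable is not closed. Its third element needs neither stopping nor re-challenge, and the protocol never says that all three must hold. A reader might infer that no event can ever be graded above Possible. That is too absolute: it holds only on the cumulative reading. This part of the reply stands, and the point is conditional for that reason.

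The first element is also loosely worded. 'Improvement' can be read as an alternative in its own right rather than as improvement on stopping, and a patient can improve after a single dose. This softens the first element but does not change the cumulative result, because re-challenge remains unobservable.

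A reader might further infer that harm would be understated to the DSMB, or that drug-caused leaks would be missed. The documents support neither. They do not say that causality grades go to the DSMB. Leak is the primary outcome, compared between randomised arms with a two-sided test, so an excess under secretin would count. Against a background leak rate of about 20%, that comparison is a better guide to drug-caused leaks than case-by-case judgement. This also stands, and it limits the importance of the point.

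What the reply does not remove is the mismatch between the scale and the design, or the missing rule for combining the elements.

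**Conclusion.** The point holds in conditional form. Two of the three elements of Probable do not fit a single-dose trial. If all are required, Possible is the highest grade available; if any one is enough, grading of the same event can differ between raters. Either way the scale does not work as a four-point scale for the events it is applied to.

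The importance is minor. The consequence lies in the safety record alone, and no trial result depends on it. The conclusion assumes that the single dose in sections 4 and 30 is the whole exposure and that no re-challenge takes place outside the written procedures. The cumulative reading is inferred from the structure of the neighbouring grades; the protocol does not state it. The concern about grading with the arm known is limited to events graded after discharge.

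**What to change.** 1. Delete the stopping, dose-reduction and re-challenge wording from Probable.
2. Define Probable by three elements that can be judged after one dose: onset clearly linked in time to the infusion; consistency with a known or expected pharmacological response; and the drug being a more likely cause than the operation or the patient's clinical state. The last should be a comparison of likelihoods. A requirement that the operation could not reasonably explain the event would exclude nearly every leak, infection, hemorrhage or reoperation after pancreatic resection and so bring back the same ceiling.
3. State that all three are required.
4. Record the causality grade before the arm is revealed, for example by holding the reveal until the 30-day assessment is complete.

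Items 1 to 3 change wording only. Item 4 changes the order of events, and its small downside is later unblinding. The endpoints, tests, sample size and interim rule are unaffected.

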Funding Source (Sponsor): ChiRhoClin, Inc, and ChiRhoClin Research Institute. This is an investigator-initiated project. ChiRhoClin, Inc. will supply the drug, Secretin. [name] will also receive a small grant from the ChiRhoClin Research Institute to support the research coordinator's salary.

1. Abstract.

Provide an abstract of the proposed research in language that can be understood by a non-scientist. The abstract should summarize the objectives of this project and the procedures to be used, with an emphasis on what will happen to the subjects. (Maximum 250 words)

Pancreatic ~~anastomotic~~-leaks complicate pancreatic resection in approximately 20% of cases. The pancreatic anastomosis or repair has been referred to as the Achilles heel of pancreatic surgery. Unfortunately, despite recognition of this problem and multiple operative techniques proposed to prevent this complication, leaks continue to represent a major cause of morbidity for patients undergoing pancreatic surgery. Treatment of leaks often requires nutritional support with total parenteral nutrition to diminish the leak in addition to invasive interventions to contain the leak with drains, stents or in severe cases, reoperation. Experiential data suggest that intra-operative infusions of secretin, a naturally occurring hormone that stimulates bicarbonate release from the pancreas, following resection but just prior to abdomen closure, may identify a leak if present. If secretin can demonstrate evidence of leaking intra-operatively, the pancreatic duct leak may be able to be fixed prior to abdominal closure. We aim to determine if giving an intra-operative infusion of secretin will allow for identification and treatment of leaks after pancreatic reconstruction and prior to abdominal closure, leading to a reduction in the rate of pancreatic ~~anastomotic~~-leaks requiring intervention. We will perform a double-blind, randomized pilot study of 176 patients undergoing pancreatic resection (pancreaticoduodenectomy and distal pancreatectomy) at Dartmouth-Hitchcock Medical Center. 88 of those patients will receive an intraoperative secretin infusion prior to abdominal closure and 88 will receive a saline placebo. Our primary outcome of interest will be the rate of pancreas duct leaks in each group as measured by the amount of amylase present in the surgical drains on or after post operative day (POD)# 3 following surgery.

2. Objectives & Hypotheses:

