List your research objectives and hypotheses.

We hypothesize that intra-operative, intravenous secretin administration will decrease the rate of pancreatic leaks in patients undergoing pancreatic resection. Our primary objective is to determine if intravenous secretin administration will decrease the amount of pancreatic leaks as defined by the 2016 ISGPS definition of postoperative pancreatic fistula, measured by drain fluid amylase on or after POD#3days following resection. Our secondary objectives are to determine if intra-operative intravenous secretin administration changes the management of the pancreatic resection margin intraoperatively or impacts length of stay (LOS)

3. Introduction:

a) Explain the background of this project so that we will understand why it is important to perform this research project. b) Summarize previously published data and pilot studies. Be sure to include a discussion of any data that do not support the study hypothesis. If a study similar to the one being

proposed has already been completed, explain why the proposed study is necessary. c) For studies designed to compare or evaluate therapies, there should be a statement of the relative advantages or disadvantages of alternative modes of therapy. d) If not obvious, explain why human subjects are necessary. Include references for all published data cited. If a formal protocol for the study exists, page references to the protocol are acceptable.

A) Pancreatic duct leaks represent a major complication of pancreatic resection surgery. With a rate of between 20% even at expert, high-volume centers, this dreaded complication causes significant morbidity for patients with associated increased hospital costs. Treatment of pancreatic duct leaks often requires pancreatic rest with intravenous nutrition, endoscopic placement of pancreatic duct stents, and/or repeat surgical operation to close the leak. Despite many advancements in terms of leak closure techniques (duct to mucosa pancreaticojejunostomy, roux-en-Y reconstruction, devices (automatic staplers/ pledgets/stents) pancreatic leaks continue to be a major problem and pancreatic surgeons continue to search for methods to prevent or diminish the severity of pancreatic leaks.

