B) Currently, there are no pilot studies which have specifically addressed whether secretin therapy can help to identify pancreatic duct leaks intra-operatively. While the drug has been used to identify leaks post-operatively using MRI (Gillams AR, Kurzawinski T, Lees WR. Diagnosis of duct disruption and assessment of pancreatic leak with dynamic secretin-stimulated MR cholangiopancreatography. AJR 2006) no previous studies have been performed. Secretin is widely available and used to stimulate pancreatic secretions from the ductal cells for many indications such as identifying the minor papilla, obtaining pancreatic fluid for cytokine analysis, and diagnosing pancreatic cancer. (Levenick JM, Andrews CL, Purich, Ed et al. A Phase II Trial of Human Secretin Infusion for Refractory Type B Pain in Chronic Pancreatitis. Pancreas 2013) It is also used to treat autism in select patients and diagnose the presence of a gastrinoma. (Williams K, Wray JA, Wheeler DM. Intravenous Secretin for Autism Spectrum Disorders. Cochrane Database Reviews 2012; Imamura M, Komoto I, Ota S. Changing treatment strategy for gastrinoma in patients with Zollinger-Ellison syndrome. World J Surg 2006).

Since 2011, patients at DHMC treated with pancreatic resection have occasionally been given intraoperative intravenous secretin to diagnose pancreatic duct leaks. While this technique has not been specifically studied in a prospective fashion, anecdotal experience demonstrates that secretin infusion can identify leaks in the operating room prior to abdominal closure. Identifying the leaks intraoperatively then allows the surgeon to alter the technique of closure or suture placement directed at the site of leakage. Our hypothesis is that secretin-assisted leak identification with localization will allow for intraoperative closure and decreased incidence and severity of clinically significant leaks in the post-operative period.

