a) *List tests, visits, and procedures performed for only research purposes. These services are outside the standard of care. They would not be performed if the individual were not a research participant, and may not be billed to a health insurance plan.*

Note: 6a information must also be in "How is this different . . ." section of the consent form.

The administration of Secretin or placebo is for research purposes only and will not be billed to the patient. Drain placement, drain amylase measurement and the two week follow-up visit are per standard of care and will be billed directly to the patient.

b) *List the tests, visits, and procedures that may be standard care, but for which the funding agency for the study is paying.*

None

c) *Will the funding agency for the study be responsible for the above costs? Yes No
If No, describe who will be responsible (i.e., department or participant).*

Secretin will be supplied by ChiRhoClin, Inc and saline placebo will be supplied by the Section of Gastroenterology and Hepatology out of research funds maintained by the primary investigators. No additional tests, visits, or procedures will be performed for research purposes only.

PLEASE ENCLOSE THE DHMC BILLING GRID/PLAN. Also enclose the schedule of events or table listing all procedures from the sponsor protocol.

7. Statistical Methods and Review Statement:

a) *Specify the primary endpoint, as well as other endpoint(s).*

Primary Objective:

1. Pancreatic leak as defined by the ISGPF definition of post-operative pancreatic leaks

Secondary Objective:

1. Assess whether intervention is performed intra-operatively on the pancreatic anastomosis following Secretin or placebo injection.
2. Assess degree to which leakage severity, as a complication, increases length of stay.

b) *State the statistical analysis plan, including all hypothesis tests (e.g., t-test, chi-square), and estimation methods related to the primary endpoint. If a formal protocol for the study exists, page references to the protocol are acceptable.*

For the analysis of the primary endpoint, a categorical variable, we will use a two-tailed Fisher's Exact test to determine a p-value. We will then be able to calculate an absolute and relative risk reduction. We will also evaluate this variable using a student's t-test for means of amylase levels in the drain fluid. We will plan on performing univariate analysis of all of the potentially contributing variables outlined in the

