CRF, and then building a multivariable logistic regression model using the categorical variable of drain amylase >3x the upper limit of normal. The data from the multivariate regression will be reported as Odds Ratios.

The secondary outcomes are both categorical and continuous variables and thus we will use the Fisher's Exact test as well as the two-tailed student's t-test. A multivariable analysis is not planned for evaluating the secondary variable.

Randomization will occur in a block format of 5 and will be generated by the primary investigators.

c) Justify the sample size, using the concepts of power, type I error, and effect size if applicable. If a formal protocol for the study exists, page references to the protocol are acceptable.

A clinically significant absolute decrease of 15% (20% to 5%) in the pancreatic duct leak rate. Based on these estimates and a two-tailed test comparing proportions using the statistical calculator (<http://homepage.stat.uiowa.edu/~rlenth/Power>), we project an estimated sample size of **176 participants (88 per arm)** to demonstrate an absolute 15% reduction in the leak rate with 80% power at a two-sided alpha level of 0.05.

8. Data and Safety Monitoring:

Describe plans for data and safety monitoring to ensure the safety of subjects and the quality of the data. As described in federal guidance "... a variety of types of monitoring may be anticipated depending on the nature, size, and complexity of the trial. In many cases, the principal investigator would be expected to perform the monitoring function." This plan should include monitoring to determine:

The progress of the trial, including periodic assessments of data quality and timeliness, participant recruitment, accrual and retention, participant risk versus benefit, and other factors that can affect study outcome. Monitoring should also consider factors external to the study when interpreting the data, such as scientific or therapeutic developments that may have an impact on the safety of the participants or the ethics of the study.

Note: This section does not request information related to sponsor study monitor visits. This section requires a description of an adequate data and safety monitoring plan.

Interim analysis will be performed once 50% (88) patients have been enrolled. If more than 66% of cases of duct leak are in a particular study group, a formal comparison between groups will be performed with the use of a two-sided stopping boundary of 0.005%.

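### The primary event is defined two ways: drain amylase >3x ULN plus a clinically relevant condition in Sections 4 and 7a, and amylase >3x ULN alone in the Section 7b regression

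*Combined protocol and SAP*

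**What the plan says.** The plan describes the primary event in several places.

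- **Section 1 (Abstract):** the rate of "pancreas duct leaks in each group as measured by the amount of amylase present in the surgical drains", on or after POD 3. It gives no cut-off and no clinical criterion.
- **Section 2:** leak "as defined by the 2016 ISGPS definition of postoperative pancreatic fistula, measured by drain fluid amylase on or after POD#3days following resection". This combines a consensus definition with an amylase measurement.
- **Section 3, part B:** the hypothesis concerns "decreased incidence and severity of clinically significant leaks in the post-operative period".
- **Section 4, definition of leak:** drain fluid of any measurable volume with amylase >3x ULN, "associated with a clinically relevant development/condition related directly to the postoperative pancreatic fistula".
- **Section 4, outcome statement:** "The primary outcome of interest will be the presence of pancreatic leaks based on the amount of drain amylase on or after POD#3". Again there is no cut-off and no clinical criterion.
- **Section 7a:** "Pancreatic leak as defined by the ISGPF definition of post-operative pancreatic leaks". The criteria are not repeated; within this document only Section 4 writes them out.
- **Section 7b:** Fisher's exact test is applied to the primary endpoint without restating the event. The text continues: "We will also evaluate this variable using a student's t-test for means of amylase levels in the drain fluid". The adjusted analysis consists of "building a multivariable logistic regression model using the categorical variable of drain amylase >3x the upper limit of normal", with no clinical criterion and no day.

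Section 7c plans for a fall in the leak rate from 20% to 5%, and Section 8 triggers an interim comparison on the split of duct-leak cases between arms. Neither says which event is meant.

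**The concern.** The two events are nested. A patient with amylase >3x ULN and no clinical consequence is a case in the regression but not under the Section 4 definition. Following the plan as written, the primary p-value and the adjusted odds ratios could be reported under one name while counting different patients.

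If the abstract and the Section 4 outcome statement are taken literally, the event in the Fisher test is also unsettled and could be chosen once results are known. The planning rates in Section 7c and the interim trigger in Section 8 inherit the ambiguity; they are not separate faults.

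**Working it through.** **1. Can the passages be reconciled?**

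- *Amylase plus clinical condition is primary.* The Section 4 definition, Section 7a, the Fisher test and the Section 3 hypothesis agree. The abstract and the Section 4 outcome statement can pass as shorthand. The Section 7b logistic model does not fit: it names a complete event and leaves out the clinical condition.
- *Amylase alone is primary.* The abstract, the Section 4 outcome statement and the logistic model agree. The Section 4 definition, and Section 7a which takes its content from it, do not.
- *Both are intended, one as supportive.* No sentence says so or says which.

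**2. The plan's own sample size.** Inputs from Section 7c: p1 = 0.20, p2 = 0.05, two-sided alpha 0.05, power 80%. With mean proportion 0.125 and difference d = 0.15:

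n = [1.960·√(2·0.125·0.875) + 0.842·√(0.20·0.80 + 0.05·0.95)]² / 0.15² = 75.1 per arm.

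With continuity correction, (n/4)·[1 + √(1 + 4/(n·d))]² = 87.9, rounded up to 88 per arm, or 176. The stated figure reproduces. Exact power of the two-sided Fisher test at 88 per arm, summed over all tables, is 83.8%.

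**3. Power if the tested event has other rates.** The documents give no share of amylase-defined leaks that are clinically relevant, so these rates are assumed (exact Fisher, 88 per arm).

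| Rates | Assumption | Power |
|---|---|---|
| 16% vs 4% | 80% of a 20%/5% amylase event | 72.1% |
| 10% vs 2.5% | 50% of a 20%/5% amylase event | 42.7% |
| 25% vs 6.25% | 20%/5% is clinical; same 75% relative reduction in the amylase event | 92.4% |
| 25% vs 10% | 20%/5% is clinical; 5 points of amylase-only events added to each arm | 69.6% |

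The direction is not determined.

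**4. How often would the choice of event change the verdict?** Model: amylase events A ~ Bin(88, p) in each arm; clinical events given A ~ Bin(A, s), with the same share s in both arms; exact sum. A disagreement is p ≤ 0.05 for one event only.

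| 20% vs 5% is the rate of | Assumed | Probability of disagreement |
|---|---|---|
| amylase alone | s = 50% | 43% |
| amylase alone | s = 65% | 27% |
| amylase alone | s = 80% | 15% |
| amylase alone | s = 90% | 8% |
| the clinical event | amylase 25% vs 6.25% | about 10% |
| the clinical event | amylase 30% vs 7.5% | 14% |
| the clinical event | amylase 40% vs 10% | 16% |

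**5. Illustration with counts out of 88 per arm (Fisher p).**

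- Amylase leaks 18 vs 4: p = 0.002.
- Clinically relevant 14 vs 3 (14/18 = 78%, 3/4 = 75%): p = 0.009.
- Clinically relevant 12 vs 3 (12/18 = 67%, 3/4 = 75%): p = 0.028.
- Clinically relevant 9 vs 2 (half in each arm): p = 0.057.

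Only the last crosses 0.05.

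**The case against.** The best defence is that the confirmatory test has a coherent reading. Section 4 defines the leak, Section 7a names that leak as the endpoint, and the Fisher test is applied to it. The amylase wording elsewhere gives only the measurement and its day, and Section 2 joins definition and measurement in just this way. What is left is the outcome of a secondary multivariable model, on which neither the primary p-value nor the 176 depends. The t-test sentence is probably loose wording for an extra continuous analysis, since a t-test of means cannot analyse a categorical event.

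Much of this stands. Section 7a works by reference only, the shorthand reading is available, and the t-test sentence is weak evidence by itself. The disagreement probabilities compare two Fisher tests that no passage plans together. They measure what is at stake if the Fisher event is left open, not the effect on the logistic model.

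The defence does not remove the conflict. Even on the favourable reading, the regression counts a different event from the primary test and is not labelled as doing so. The favourable reading is also the reader's inference: the sentence that announces the primary outcome mentions amylase and nothing else.

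**Conclusion.** The concern holds. The plan gives two nested definitions of its primary event, and no reading reconciles all the places where the event appears. The sample-size arithmetic is correct for 20% vs 5%, and no loss of power is shown: power for the tested event could be lower or higher than planned, depending on which event has the 20% rate.

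A change of verdict between the two events is the minority case under every assumption tried, 8% to 43% or about 10% to 16%. Those figures rest on an assumed clinically relevant share, equal in both arms, and on a constant 75% relative reduction. The documents supply neither the share nor that reduction for both events.

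This has to be fixed because it concerns the definition of the primary endpoint, which cannot be settled credibly once unblinded results are available.

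**What to change.** Before any unblinded data are seen:

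1. Name one primary event with its POD window. Use it in the abstract, Sections 2, 4 and 7a, the Fisher test, the logistic model and the Section 8 interim trigger. Either event resolves the conflict.
2. Make the other definition a named secondary endpoint.
3. Describe the t-test of mean drain amylase as a separate supportive analysis, not as an analysis of the primary variable.
4. State in Section 7c which event the 20% and 5% refer to, or restate the power for the chosen event.

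Only if the clinically relevant event is chosen, two further steps apply. State which conditions qualify: Section 4 lists leak sequelae followed for 30 days but does not tie them to the definition. Also hold back the assignments until day-30 follow-up is complete, because Section 4 reveals them at discharge, while such events can still be assessed.

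The cost is protocol and SAP wording and possibly a less favourable stated power. For the clinically relevant event, add a written list of qualifying conditions, a later reveal, and a check that the case report form, which is not in the text reviewed, captures the items needed.
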